# LIST OF ABBREVIATIONS

BD Twice Daily

HC Health Clinic

MR Modified Release

PRN When necessary

OD Once Daily

TDS Three times a day

#### **CHAPTER 1**

#### INTRODUCTION

### 1.1 Study Background

The complex processes and human interactions involved in transitions of care between different healthcare settings harbour a great risk of medication errors, particularly among patients with multiple comorbidities and complex medication regimens. Medication reconciliation is thus one of the key strategies to improve medication safety across transitions of care. It is the formal process of creating the accurate and complete list of medications through the partnership between healthcare providers and patients at all interfaces of cares to reduce potential medication errors and patient harm (1).

The four steps involved in medication reconciliation are: (1) verification: obtain the current medication list; (2) clarification: check the medication dosages; (3) reconciliation: compare and document newly prescribed and previous medications and (4) transmission: communicate the updated and verified medication list to the next healthcare provider (1). These processes involve multiple stakeholders (doctors, nurses, pharmacists, and patients) and all parties are interdependent and accounted to improve transitional care medication safety.

#### 1.2 Problem Statement

Numerous studies showed that medication discrepancies and errors are prevalent during admission and discharge (2, 3). Reconciliation of patient's past medications upon admission has been an established routine for more than a decade among clinical pharmacists, especially in the general medical wards at tertiary healthcare institutions in Malaysia. Nonetheless, medication reconciliation upon and after hospital discharge has not been implemented in a

structured process, potentially putting patients at risk of medication errors during transitions of care from hospital to the primary healthcare setting.

Very often, local healthcare providers find it difficult to retrieve previous medical records as the healthcare information system has not been integrated across the healthcare facilities in Malaysia. This problem gets worse when patients do not compile and keep their discharge summary properly when they are discharged and followed up at the primary health clinics. Tracing the record is either involving a lengthy process or to no avail due to vague information provided by the patient or caregiver. The referred facility could have continued with the previous medications without knowing the patient's latest disease state. Thus, scattered sources of medication information among different levels of care and lack of integrated computerised healthcare information system pose a great challenge to ensure medication safety. Besides the above barriers, some other potential predictive factors associated with medication errors were patient characteristics, clinical conditions, number of medications, specific pharmacological agents, length of hospital stay and inexperienced prescribers (4).

To the best of our knowledge, there has been no study conducted in Malaysia, that aims to reduce the medication errors when patients were discharged from a tertiary or secondary hospital to primary health clinic. Past studies conducted in western countries provided limited generalizable evidence on the efficacy of their interventions in dealing with the problem in local context due to different healthcare delivery system and practices (5, 6). In addition, relevant studies conducted in Malaysia merely explore the prevalence and factors contributing to the problem and the perception of stakeholders on the feasibility of implementing medication reconciliation program upon hospital discharge (7, 8). Hence, this warrants the development of an effective measure to overcome the problem. Apart from exploring the prevalence and predictors of medication discrepancies upon discharge, an innovative intervention that aims to

reduce the medication discrepancies upon transition of care will also be introduced and implemented at the major divisions in Sarawak as our first move.

# 1.3 Research Question

The research question of the current study is "is MedBook Portal effective in reducing medication discrepancies upon transition of care from hospitals to primary health clinics?".

# 1.4 Objectives

In general, this study aims to assess the prevalence of medication discrepancies in the first prescription upon transition of care from hospitals to primary health clinics, comparing MedBook Portal to standard care.

In specific, this study aimed:

- To assess the prevalence of medication discrepancies in the first prescription upon transition of care from hospitals to primary health clinics, comparing MedBook Portal to standard care.
- ii. To determine the prevalence of the type of medication discrepancies in the first prescription upon transition of care from hospitals to primary health clinics.
- iii. To determine the prevalence of the type of medication discrepancies in discharge prescription.
- iv. To identify the predictors associated with medication discrepancies in the first prescription upon transition of care from hospitals to primary health clinics.
- v. To identify the predictors associated with medication discrepancies in discharge prescription.

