### 1.5 Study Hypotheses

The study hypotheses are formulated based on the study specific objectives. For the first specific objective, the hypothesis is about the impact of MedBook Portal on the prevalence of medication discrepancies in the first prescription upon transition of care from hospitals to primary health clinics.

In terms of the second and third objectives, the hypotheses are based on the previous study conducted the hypotheses are based on the previous study conducted by Law and Chong (2017) in Malaysia. This study reported 49% of the discharge prescription were found to have a least one medication discrepancies (8).

For the fourth and fifth specific objectives, there are five variables are included as the secondary outcome of the study, namely age of patient, number of comorbidities, number of medications, type of medication (ATC categorization), and experience of prescriber (category of prescriber). All the five secondary outcomes are hypothesized to be the predictors of medication discrepancies. The hypotheses are tabulated in Table 1.1.

Table 1.1: Study Hypotheses

Specific objective 1: To assess the prevalence of medication discrepancies in the first prescription upon transition of care from hospitals to primary health clinics, comparing MedBook Portal to standard care.

H1a

There will be a significant difference of medication discrepancies rates between the intervention group and the control group after the intervention. The estimated difference of the medication discrepancies rates is 15%, with intervention group having lower medication discrepancies rates than control group.

Specific objective 2: To determine the prevalence of the type of medication discrepancies in the first prescription upon transition of care from hospitals to primary health clinics.

H2a

The prevalence of each type of medication discrepancy ranges from 5 - 60%, with Drug omission as the most common medication discrepancy in the first prescription upon transition of care from hospitals to primary health clinics.

Specific objective 3: To determine the prevalence of the type of medication discrepancies in discharge prescription.

Н3а

The prevalence of each type of medication discrepancy ranges from 5-60%, with Drug omission as the most common medication discrepancy in discharge prescription.

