#### **CHAPTER 2**

#### **METHODOLOGY**

# 2.1 Study Design

Given the nature of the research question, a randomised controlled trial is developed to compare the prevalence of medication discrepancies in the first prescription upon transition of care from hospitals to primary health clinics between MedBook Portal and standard care. This study is a prospective and multicentre randomised controlled trial with a 1:1 allocation ratio to two groups, namely the intervention group and the control group. MedBook portal is a webpage that enables sharing of patient medication profile among healthcare facilities under the Ministry of Health.

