### 2.5 Sample Size Calculation

This study aims to compare the prevalence of medication discrepancies in the first prescription upon transition of care from hospitals to primary health clinics between MedBook Portal and standard care. Hence, a two-tailed z-test of proportion between two groups with 80% power and a 5% of level significance will be used (10). The prevalence of medication discrepancies upon discharge reported in a previous study is 49% (8). We estimate the reduction of medication discrepancies via implementation of MedBook is 15%. Thus, a sample size of 322 subjects, 161 subjects in each group, is sufficient to detect a clinically importance difference of 15% between groups. However, with the estimation of a 20% loss to follow up, a total of 386 subjects will be recruited.

In addition, this study also aims to ascertain the prevalence of medication discrepancies and type of medication discrepancies in discharge prescription and in the first prescription upon transition of care from hospitals to primary health clinics. Sample size is calculated by using the following formula (11):

$$n = \frac{Z^2 P(1-P)}{d^2}$$

where n = sample size,

Z = Z statistic for a level of confidence,

P = expected prevalence or proportion

d = precision

By determining the Z = 1.96 for 95% CI and d = 0.05, the minimum sample size is 384. Based on the above sample size calculation, a total of 386 patients will be recruited. The sample size allocation for each hospital is determined on a pro-rata basis based on the total bed numbers in general medical wards and Bed Occupancy Rate (Table 2.4).

**Table 2.4:** Sample Size Allocation Of Each Hospitals

Public Major	Wards	Total	Bed	Sample
Hospitals		Bed	Occupancy	Size
		Numbers	Rate (%)	Allocation
Sarawak General	Male General Ward	48	114.4	144
Hospital	Female General Ward	48	102.0	
Sibu Hospital	Male General Ward 1	36	62.2	106
	Male General Ward 2	36	73.4	
	Female General Ward	32	83.5	
Miri Hospital	Male General Ward	29	114.1	72
	Female General Ward	30	62.8	
Sarikei Hospital	Male General Ward	35	82.4	64
	Female General Ward	35	50.2	
Total	-	329	-	386

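### Objective ii names no arm, and its ±5-point precision for discrepancy types in the first clinic prescription can be reached only by combining two arms that the plan expects to differ

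*Combined protocol and SAP*

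**What the plan says.** - **Objective ii (section 1.4)** is "To determine the prevalence of the type of medication discrepancies in the first prescription upon transition of care". Objective i, just above it, closes by contrasting MedBook with standard care. Objective ii has no such clause.
- **H2a (section 1.5, Table 1.1)** gives one range and one ranking, again with no arm: "The prevalence of each type of medication discrepancy ranges from 5 - 60%, with Drug omission as the most common medication discrepancy".
- **H1a (same table)** says of overall discrepancy rates: "The estimated difference of the medication discrepancies rates is 15%, with intervention group having lower medication discrepancies rates than control group".
- **Section 2.5** applies a single-proportion formula to the "prevalence of medication discrepancies and type of medication discrepancies in discharge prescription and in the first prescription upon transition of care from hospitals". It concludes "By determining the Z = 1.96 for 95% CI and d = 0.05, the minimum sample size is 384", and then "Based on the above sample size calculation, a total of 386 patients will be recruited".
- **Section 2.1** describes a trial "with a 1:1 allocation ratio to two groups, namely the intervention group and the control group".
- **Section 2.14** plans a comparison between arms for the primary outcome only. For discrepancy types it says that they will be collected. Section 2.15 has a general sentence on chi-square tests and does not mention type by arm.
- **Section 2.9** places discharge reconciliation before randomisation. Under sections 2.11 and 2.12, the clinic doctor consults the portal list for intervention patients and cannot do so for control patients.

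**The concern.** A single prevalence with a ±5-point interval is meaningful when the sample comes from one population. That is true of the discharge prescription, which is assessed before allocation. It is not true of the first clinic prescription: by then half the patients are under an intervention designed to reduce discrepancies. If the types are tabulated over everyone, each percentage is a mixture weighted by the 1:1 allocation ratio and belongs to no care setting. A reader looking for the pattern of discrepancies in local practice would take it as that pattern. On the plan's own hypothesis, types that the portal reduces would be understated for standard care and overstated for MedBook.

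The stated precision is a second problem. The 384 carries no allowance for patients who never reach the clinic, and no arm comes near 384.

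**Working it through.** **Inputs.** From section 2.5: Z = 1.96, d = 0.05, n = 384, 386 recruited, 20% loss, 49% planning prevalence, 15-point reduction (so 49% v 34%). From section 2.1: 1:1 allocation, so 386/2 = 193 per arm. The value of P behind the 384 is not restated in the plan, so both candidates are tried. Assumptions: loss is equal in the two arms, and prevalence is counted per prescription.

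**1. Reproduce the plan's figure.** n = Z²P(1−P)/d².
- P = 0.49: 3.8416 × 0.2499 / 0.0025 = 384.0
- P = 0.50: 3.8416 × 0.2500 / 0.0025 = 384.2

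The 384 reproduces on either value.

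**2. Which sample meets it?** Half-width = 1.96 × √(P(1−P)/n), at P = 0.49.
- Both arms, n = 386: 1.96 × √(0.2499/386) = ±4.99 points
- One arm, n = 193: 1.96 × √(0.2499/193) = ±7.05, or about ±7.1 points

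Only the combined sample reaches ±5. Within one arm, ±5 at P = 0.49 would need 385 patients in that arm.

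**3. Apply the plan's own loss.** 386 × 0.8 = 308.8, about 309 clinic prescriptions; 193 × 0.8 = 154.4, about 154 per arm.
- Combined, n = 309, P = 0.49: 1.96 × √(0.2499/309) = ±5.6 points. At the mixture value of 41.5% it is ±5.5.
- One arm, n = 154, P = 0.49: 1.96 × √(0.2499/154) = ±7.9 points

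At the planning prevalence, ±5 is missed on either reading.

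**4. Rarer types.** H2a's range starts at 5%, and half-width shrinks as P moves away from 0.5.

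| P | One arm, n = 193 | One arm, n = 154 |
|---|---|---|
| 0.10 | ±4.2 | ±4.7 |
| 0.20 | ±5.6 | ±6.3 |
| 0.49 | ±7.1 | ±7.9 |

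**5. Size of the mixing.** With equal arms, combined = (p_control + p_MedBook)/2, so the distance from either arm is (p_control − p_MedBook)/2.
- Overall prevalence: (49% + 34%)/2 = 41.5%, which is 15/2 = 7.5 points from each arm. This shows the mechanism for the overall rate. It is not a result for any type.
- By type, the documents give no rates by arm. Suppose, for illustration only, that every type falls in the overall proportion 34/49 = 0.694. The shift is then p_control × (1 − 0.694)/2 = 0.153 × p_control. A control rate of 10% gives 1.5 points, 20% gives 3.1, and 40% gives 6.1. The shift passes 5 points only above about 33% (5/0.153).

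**The case against.** The strongest reply is that the plan never says it will combine the arms. The general objective compares MedBook with standard care. Section 2.15 says categorical variables are compared by chi-square, and in a two-group trial discrepancy type could be one of them. The clinic form in Appendix B records patient ID and discrepancy type, and section 2.10 has the coordinator hold the code with group assignment, so tabulation by arm remains possible. This part stands: combining is inferred from an arm-free objective and hypothesis, and from 384 being matched to 386. It does not rescue section 2.5. If by-arm reporting is intended, the 384 does not support it; if combining is intended, the result is a mixture.

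A reader might also infer more than the documents support:

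- **That overall prevalence in the first clinic prescription will be misreported.** It will not. Objective i and section 2.14 compare it by arm. Objective ii concerns each type.
- **That each type is displaced by 7.5 points.** That figure comes from the overall rates. Under proportional reductions, less common types move far less.
- **That ±5 points is unattainable in either arm.** It is attainable for rarer types, as the 10% row shows.
- **That omission would be pulled down most, upsetting H2a's ranking.** Nothing in the documents says which types the portal prevents best. With proportional reductions the ranking does not change; it could change only if effects differ by type.

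Lastly, an overall figure shown beside by-arm figures does no harm if it is labelled for what it is.

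**Conclusion.** The point holds in limited form. Objective ii and H2a leave the arm unspecified for a quantity measured after allocation. The only sample size offered for that aim relies on combining arms that H1a expects to differ. A combined type prevalence would be off from each arm by half that type's difference between arms, an amount the documents do not allow one to calculate. At the planning prevalence, the clinic prescription gets about ±5.6 points combined after loss, or ±7.1 to ±7.9 in one arm, instead of ±5.

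These figures assume equal loss of 20% in each arm and a per-prescription denominator. The second assumption needs confirming. H2a's upper limit of 60% for a single type exceeds the 49% overall prevalence used for planning, so types may be meant as shares of discrepancies. In that case the half-widths above would not apply as they stand.

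Objective iii is unaffected, because discharge discrepancies are recorded before randomisation and combining is valid there. The primary comparison is also untouched. This is a correction to a secondary descriptive objective that should be made before analysis.

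**What to change.** 1. In section 1.4 (ii), H2a and section 2.14, state that the prevalence of each discrepancy type in the first clinic prescription is reported by arm with 95% intervals, and that the control arm is the estimate for standard care. Label any overall figure as a trial mix under 1:1 allocation.
2. In section 2.5, limit the 384 and ±5-point statement to the discharge prescription. For the clinic prescription, state the per-arm precision as at most about ±7 to 8 points, depending on P (for example ±4.2 to ±4.7 at 10%).
3. State the denominator for type (prescriptions or discrepancies), so that the stated precision matches the quantity reported.

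The cost is wording only, with no added patients, visits or data items. The downside is a less favourable stated precision for a secondary descriptive objective.

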### 1.5 Study Hypotheses

The study hypotheses are formulated based on the study specific objectives. For the first specific objective, the hypothesis is about the impact of MedBook Portal on the prevalence of medication discrepancies in the first prescription upon transition of care from hospitals to primary health clinics.

In terms of the second and third objectives, the hypotheses are based on the previous study conducted the hypotheses are based on the previous study conducted by Law and Chong (2017) in Malaysia. This study reported 49% of the discharge prescription were found to have a least one medication discrepancies (8).

For the fourth and fifth specific objectives, there are five variables are included as the secondary outcome of the study, namely age of patient, number of comorbidities, number of medications, type of medication (ATC categorization), and experience of prescriber (category of prescriber). All the five secondary outcomes are hypothesized to be the predictors of medication discrepancies. The hypotheses are tabulated in Table 1.1.

Table 1.1: Study Hypotheses

Specific objective 1: To assess the prevalence of medication discrepancies in the first prescription upon transition of care from hospitals to primary health clinics, comparing MedBook Portal to standard care.

H1a

There will be a significant difference of medication discrepancies rates between the intervention group and the control group after the intervention. The estimated difference of the medication discrepancies rates is 15%, with intervention group having lower medication discrepancies rates than control group.

Specific objective 2: To determine the prevalence of the type of medication discrepancies in the first prescription upon transition of care from hospitals to primary health clinics.

H2a

The prevalence of each type of medication discrepancy ranges from 5 - 60%, with Drug omission as the most common medication discrepancy in the first prescription upon transition of care from hospitals to primary health clinics.

Specific objective 3: To determine the prevalence of the type of medication discrepancies in discharge prescription.

Н3а

The prevalence of each type of medication discrepancy ranges from 5-60%, with Drug omission as the most common medication discrepancy in discharge prescription.

Specific objective 4: To identify the predictors associated with medication discrepancies in the first prescription upon transition of care from hospitals to primary health clinics.

H4a

There is a significant association between age of patient, number of comorbidities, number of medications, type of medication (ATC categorization), experienced of prescriber (category of prescriber) and medication discrepancy in the first prescription upon transition of care from hospitals to primary health clinics.

# continued

Specific objective 5: To identify the predictors associated with medication discrepancies in discharge prescriptions.

H5a There is a significant association between age of patient, number of comorbidities, number of medications, type of medication (ATC categorization), experience of prescriber (category of prescriber) and medication discrepancy in discharge prescription.

# 1.6 Conceptual Framework

The conceptual framework of the study is based on the rationale and design of the "Multicenter Medication Reconciliation Quality Improvement Study" (MARQUIS) (9). Bidirectional medication information transfer across settings via electronic health records shall ease the medication reconciliation process. Subsequently, a reduction in medication discrepancy will be the outcome of the study. In addition, predictors correlated with medication discrepancies might impact the prevalence of medication discrepancies. Figure 1.1 depicts the conceptual framework of the study.

[figure not shown]

Figure 1.1: Conceptual Framework

### 1.7 Significance of Research

Proper documentation in hospital discharge summary is essential to ensure continuity of care as patient is involved in multiple care transitions. At hospital discharge, reconciliation is done by checking pre-admission medication list and inpatient medication chart prior to the finalisation of the discharge medication list. Pharmacists serve as the last row of defence to ensure the accuracy of the prescribed medications, couple with discharge counselling to enhance medication understanding and adherence.

In Sarawak, every patient who undergoes medical follow-up at a primary public healthcare setting possesses a personal medical record which will be presented to the doctor during health clinic follow-up and upon hospital admission. Nonetheless, the information upon hospital discharge and clinic follow-up at the secondary or tertiary healthcare setting are not incorporated in the same personal medical record. The discharge summary is provided in separate copies, and the record of clinic follow-up at secondary or tertiary healthcare settings is kept at the clinic. Due to the scattered information, the redundancy of medications with the same or different dosing regimens from various clinics follows up across primary to tertiary healthcare settings is a common issue. Subsequently, this has created confusion and dilemma for the patients as to which regimen to follow, deprived their rights to a holistic treatment approach and jeopardized their health condition.

Recognising the missing part in the healthcare system, enhanced focus on medication reconciliation upon and after hospital discharge could bridge the gap to promote medication and patient safety. By implementing the medication reconciliation upon hospital discharge by pharmacists based in the wards, coupling with patient education and discharge medication plan communication, and followed with the introduction of a medication portal to the prescriber upon discharge which eventually serve as a compilation of personal medication records.

Subsequently, during clinic follow-up, medication reconciliation and updating of the patient medication list in the medication portal will be carried out by the pharmacist in the primary healthcare setting.

In a nutshell, this study may greatly benefit the patients through anticipated medication discrepancies reduction via an innovative intervention. Besides, this intervention is also deemed easy to implement, thus enhancing the duplications and generalizability of the intervention to the healthcare facilities in Malaysia.

